5.0 BACKGROUND INFORMATION AND SCIENTIFIC RATIONALE

Real World Evidence can provide information on how factors such as clinical setting, health care provider, and health-system characteristics influence treatment effects and outcomes. Importantly, the use of such evidence has the potential to allow researchers to answer these questions efficiently, while yielding answers relevant to broader populations of patients. Prospective registries with planned external controls and high-quality data collection have been accepted for regulatory purposes in the evaluation of medical devices.¹ Ideally, patient registries collect data in a comprehensive manner and, therefore, produce outcome results that may be generalizable to a wide range of patients.²

For the NEUWAVE Microwave Ablation System, the microwave ablation procedure parameters (including time, power, number and type of probes used) necessary to obtain desired short-term and long-term results across a range of target lesion characteristics (including size, location, co-morbidities, previous treatments, etc.) have not been studied in a systematic manner, nor is it known how operator factors affect results.

6.0 REGISTRY OBJECTIVES AND ENDPOINTS

6.1 Primary Objective

The primary objective of this registry is to compile data that will be analyzed at various timepoints, to understand the impact of selected parameters on procedure and patient outcomes. The database will capture data related to (1) Ablation Procedure parameters, (2) Patient parameters, and (3) Healthcare Provider parameters.

6.2 Primary Endpoints

The primary endpoints of this registry are below, based on different points in time:

Perioperative endpoint-

1. Technical success, defined as ablation of the target lesion(s) according to the protocol and covered completely, with an adequate margin, as defined by the performing physician (i.e. the ablation zone completely overlaps or encompasses the target lesion(s) plus an ablative margin), as assessed by CT, MRI, PET, US, and/or X-ray, immediately following the procedure.

Short term endpoint-

2. Technique efficacy, ablation of the target lesion(s) according to the protocol and covered completely, with an adequate margin, as defined by the performing physician (i.e., the ablation zone completely overlaps or encompasses the target lesion(s) plus an ablative margin), as assessed by CT, MRI, PET, US, and/or X-ray, at Visit 3 (between 7 days and less than 3 months post-ablation).

Long term endpoint-

3. Target lesion recurrence (local recurrence) rate evaluated at every visit after ablation of the target lesion(s), and overall evaluation at the 5-year follow-up, as assessed by CT, MRI, PET, US, and/or X-ray.

6.3 Secondary Endpoints

The secondary endpoints of this registry are:

1. Secondary efficacy rate, defined as the percentage of soft tissue lesions that have undergone successful repeat ablations (target or non-target) following identification of local soft tissue lesion progression. A successful repeat ablation will be defined as ablation of the lesion according to the protocol and covered completely, with an adequate margin, as defined by the performing physician (i.e. the ablation zone completely overlaps or encompasses the lesion plus an ablative margin), as assessed by CT, MRI, PET, US, and/or X-ray, immediately following the procedure.
2. Regional recurrence rate at a separate location in the liver (outside the initial treatment site(s)), evaluated at every visit after ablation of the target lesion(s), and overall evaluation at the 5-year follow-up, as assessed by CT, MRI, PET, US, and/or X-ray.
3. Recurrence-free survival, evaluated at every visit after ablation of the target lesion(s), and overall evaluation at the 5-year follow-up, as assessed by CT, MRI, PET, US, and/or X-ray.
4. Overall survival, evaluated at every visit after ablation of the target lesion(s), and overall evaluation at the 5-year follow-up.
5. Assess economic impact of ablation by capturing procedure-related items such as: complete procedure duration, ablation duration, number of ablations, length of hospital stay, and number and types of probes used.
6. Incidence of adverse events (AEs) (SAEs) that are deemed at least unlikely related to the procedure or device and all serious adverse events (SAEs) from the start of the ablation procedure through the end of the study.
7. Two QOL questionnaires: European Organization for Research and Treatment of Cancer (EORTC) QLQ-C30 and liver-specific QLQ-HCC18.

Note: These two questionnaires were chosen as tools to assess overall health status/quality of life in the patient population with soft-tissue liver lesions.

8. Numeric Pain Rating Score.

7.0 REGISTRY DESIGN

7.1 Overall Registry Design and Plan – Description

This is a multicenter, observational registry that follows patients for a total of 5 years from the date of the first liver ablation procedure with the NEUWAVE Microwave Ablation System. The data gathered from participating sites will be available to be analyzed to develop ablation parameter guidance for ablation approaches under varying patient liver tissue conditions and liver lesions.

This is an “umbrella registry,” which was included as an optional component in other NEUWAVE studies; hence, data from consenting patients who are or will be enrolled in other NEUWAVE soft tissue liver lesion ablation studies will be included in this registry. All other patients will be enrolled and followed prospectively, enrolled retrospectively with prospective, longitudinal follow up, or enrolled retrospectively with all retrospective follow up.

7.2 Enrollment

The goal is to create a registry with enrollment ongoing until there are an adequate number of patients with which a statistically sound analysis could be performed. Enrollment for this study will include at least 1,500 patients throughout the world who underwent or are undergoing microwave ablation of one or more soft tissue liver lesions using the NEUWAVE Microwave Ablation System or the NEUWAVE Microwave Ablation System with Ablation Confirmation.

7.3 Inclusion Criteria

1. Patients who underwent or are scheduled to undergo a microwave ablation of one or more liver lesions with the NEUWAVE Microwave Ablation System per the device's Instructions for Use (IFU).
2. Patients with signed informed consent (or waiver approved by IRB/EC) who are willing to comply with the assessment schedule, and willing to have data included in the database.
3. Patients \geq 22 years old at the time of informed consent (or waiver approved by IRB/EC).

7.4 Exclusion Criteria

1. Patients with a life expectancy of less than 1 year, in the opinion of the treating physician.
2. Use of microwave ablation purely as a transection tool, rather than focused liver lesion ablation.

3. Patient is currently participating, or planning to participate, in another NeuWave/Ethicon-funded clinical trial or registry studying microwave ablation in the liver. Note: roll-over patients from previous NeuWave trials are permitted.

7.5 Prior and Concomitant Therapy

Patients may continue with their current medical care throughout the duration of the registry, including medications. Relevant concomitant medications will be recorded on the relevant eCRF page. Relevant concomitant medications include: chemotherapy, immunotherapy, blood-thinning or coagulation, NSAIDs, those medications used to treat AEs, those used for hepatitis (if concurrently treating), and any others that are relevant in the opinion of the investigator.

7.6 Screen Failures

All patients signing consent who do not meet the eligibility or who do not have the ablation procedure initiated will be recorded as screen failures. The relevant eCRF pages (i.e. demographics and reason for screen failure) will be completed for all screen failure patients and thereby included in the registry database.

7.7 Removal of Patients from the Registry

In accordance with the current revision of the Declaration of Helsinki and the Code of Federal Regulations, a patient has the right to withdraw from the registry at any time for any reason without prejudice to his/her future medical care by the physician or the institution. Should a patient (or patient's legally authorized guardian/representative) decide to withdraw from the registry, all efforts will be made to collect all AEs the patient may have experienced.

Participation may be terminated prior to completing the registry for any of the reasons listed below (reasons that do not fit the categories below will be documented as "other").

Withdrawal of Consent:

If a patient chooses to withdraw early from the registry, the patient should contact the site, which will then complete the Subject Completion/Discontinuation eCRF page. When a patient's participation is terminated prior to completing the registry, the reason for withdrawal is to be documented on the eCRF and in the source documentation.

Investigator Decision for Patient Termination:

The Investigator may withdraw a patient for any safety reason, including, but not limited to, the following reasons:

1. Inability of Investigator to locate and target the soft tissue liver lesion.
2. Inability of patient to tolerate the anesthesia.

Note: If a patient experiences an AE during probe puncture and is not ablated, this patient should be followed until AE resolution. If no AE occurred during probe puncture and the patient could not be ablated, the patient should be discontinued.

Death:

When available, the cause of death should be documented in the AE eCRF. The Subject Completion/Discontinuation eCRF also must be completed.

Lost to follow-up:

All patients should be encouraged to return for clinic visits for evaluation during the registry follow-up period. After all attempts to contact the patient have failed and after 2 consecutive missed visits to the site, a patient will be considered lost to follow up. Should the patient return to the site, their status in the database may be updated accordingly and data continue to be collected. For patients who are definitively lost to follow-up, the reason for early termination will be completed in the Subject Completion/Discontinuation eCRF.

Site Termination or Registry Termination:

The Sponsor may terminate a site or the registry at any time. When this occurs all patients at the site will be withdrawn and documented as “early termination.” Reasons for site or registry termination may include, but are not limited, to the following:

1. Administrative concerns (e.g., inadequate patient enrollment, investigator/institution non-compliance, change of business strategy, etc.).
2. Safety issues including those due to non-compliance, which substantially affect the risk-to-benefit ratio of the registry patients at a site or for the registry as a whole.
3. Regulatory body mandates.

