4.0 PROTOCOL SUMMARY

Full Title	A Multicenter Observational Registry to Develop Ablation Parameter Guidance for Microwave Liver Ablation of Soft Tissue Lesions
Protocol Number	NEU_2017_04
Short Title	NOLA (NeuWave Observational Liver Ablation) Registry
IDE/IND number	N/A
Sponsor	NeuWave Medical, Inc.
Indication	Ablation (coagulation) of soft tissue in percutaneous, open surgical, and in conjunction with laparoscopic surgical settings, including the partial or complete ablation of non-resectable liver tumors.
Registry Article Description	
 • NEUWAVE Microwave Ablation System and Accessories (originally marketed as the “Certus 240 140 2.45GHz Ablation System and Accessories”; hereafter referred to as “NEUWAVE Microwave Ablation System”). • NEUWAVE Microwave Ablation System with Ablation Confirmation.
Registry Design	This is a multicenter, observational registry that follows patients for a total of 5 years from the date of the first liver ablation procedure with the NEUWAVE Microwave Ablation System.
Sample Size	N = up to 1500 patients ablated.
Registry Population	Patients with at least one soft-tissue liver lesion ablated with the NEUWAVE Microwave Ablation System or NEUWAVE Microwave Ablation System with Ablation Confirmation.
Geographic Areas	Starting at sites in the United States and expanding to regions where NEUWAVE Microwave Ablation Systems are available, including EMEA and Asia.
Registry Duration	Enrollment: ~2 years Follow up: 5 years
Procedure(s) Description	Patients who meet the eligibility criteria will undergo microwave ablation (MWA) with the NEUWAVE Microwave Ablation System with or without Ablation Confirmation of at least one soft-tissue liver lesion, in accordance with the study site’s standard-of-care (SOC) practices.
Primary Objective	The primary objective of this registry is to compile data that will be analyzed at various timepoints, to understand the impact of selected parameters on procedure/patient outcomes.

Primary Endpoints	
 • Technical success (perioperative endpoint) • Technique efficacy (short term endpoint) • Target lesion recurrence (local recurrence) rate (long term endpoint)

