12.2 Visit 2 – Ablation Procedure

Patients will be under anesthesia during the procedure per the site's SOC. On the day of ablation, SOC imaging will be done at the timepoints listed in the section below.

Pre-ablation

Data collected before the procedure:

- Evaluate ECOG performance status (prior to ablation).

- Confirm that the patient still meets inclusion and exclusion criteria.
- Record all relevant concomitant medications: Relevant concomitant medications include: chemotherapy, immunotherapy, blood-thinning or coagulation, NSAIDs, those used for hepatitis (if concurrently treating), and any others that are relevant in the opinion of the investigator.
- QOL questionnaires, using EORTC QLQ-C30 and liver-specific QLQ-HCC18. The questionnaires may be administered up to 72 hours prior to the ablation procedure. The questionnaires may also be administered over the phone, as needed.
- Pain score, using the Numeric Pain Rating Scale. The questionnaire may be administered up to 72 hours prior to the ablation procedure. The questionnaire may also be administered over the phone, as needed.
- SOC imaging (i.e. CT, MRI, US) to determine soft tissue liver lesion details (e.g. size, location, shape, stage), if performed as part of site's routine SOC.

During ablation

Use SOC imaging to guide the microwave ablation probe to the target soft tissue liver lesion(s) and insert the probe into the lesion(s). Data collected during the procedure:

- Record ablation procedure details as outlined in section 19.1, subsection 1
- Record any applicable AEs/SAEs.

Note: When available, some of the above ablation procedure details will be provided to the site via a report generated from the Call Home Database. The site will review the Call Home report and enter the procedure details into the clinical database, as applicable.

Post-ablation

After the ablation procedure, the following assessments will occur:

- Pain score using the Numeric Pain Rating Scale. The post-ablation pain score must be administered on the day of ablation (Day 0). The questionnaire may be administered over the phone, as needed.
- Relevant concomitant procedures (i.e. liver or lesion-related).
- Record all applicable AEs/SAEs and product complaints.

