13.0 ASSESSMENT OF SAFETY

Patients will be assessed and monitored for all AEs that are deemed at least unlikely related to the procedure or device from the day of ablation (from the time of first probe insertion) through the 5-year follow-up visit and all SAEs.

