13.2 Reporting Adverse Events

All procedure-related and device-related AEs (non-serious) and all SAEs from the time of the first probe placement through study completion (Visit 14), or to the time of early withdrawal of the study, must be reported in the AE eCRF. The Investigator will evaluate the severity of the event and its relatedness to the registry device or procedure.

The Investigator is required to report all applicable non-serious AEs to the Sponsor within 2 weeks of becoming aware of the adverse event(s). All SAEs are to be reported as soon as possible, but no later than 72 hours after becoming aware of the event, regardless of relationship to the device or study procedure.

The study site will report applicable AEs and all SAEs to the Sponsor by entering the event into the EDC system via the Adverse Event eCRF, which will trigger an automated email to the Sponsor. Additional information, including the Investigator's assessment, may be added to the eCRF later. Any necessary medical management of the event will be recorded in the patient's medical record/source document. If the Sponsor requires supporting documentation or other information, the Sponsor will contact the study site.

Data related to AEs and SAEs will be collected until event resolution, until the event is considered stable, or until all attempts to determine the resolution of the event are exhausted. All AEs and SAEs that are unresolved at study completion (or early termination) will be recorded as ongoing at study end.

In addition, the following information should be recorded:

- Onset date
- Resolution date or date of death
- Action taken
- Event status (ongoing at registry end or resolved)
- Relationship of AE to the ablation device used in the registry
- Relationship of AE to the registry procedure
- Indication of seriousness.
- Was AE anticipated or not (only for serious, device-related AEs)

The report of an AE or SAE by a site does not constitute an admission that registry personnel or the user facility (hospital/clinic) caused or contributed to the event. The site is responsible for submitting AEs to the reviewing IRB/EC, per their IRB/EC procedures.

For retrospectively enrolled patients, the site should review patient medical records (i.e. through chart review) to look for reportable AEs/SAEs. Collection of AE data and reporting requirements will be the same for retrospective events, however, Sponsor reporting timelines do not apply.

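### A prospective patient punctured but not ablated is discontinued if no AE is seen during puncture, so a complication that first appears later need not be reported

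*Protocol*

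**What the plan says.** Protocol 13.0 sets the safety window as "from the day of ablation (from the time of first probe insertion) through the 5-year follow-up visit and all SAEs". Protocol 13.2 requires non-serious related AEs and all SAEs to be reported "from the time of the first probe placement through study completion (Visit 14), or to the time of early withdrawal of the study".

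Protocol 7.7, under the investigator's decision to terminate a patient, has a note on patients who are punctured but not ablated. It has two branches. If an AE occurs during puncture, the patient is followed until it resolves. Otherwise: "If no AE occurred during probe puncture and the patient could not be ablated, the patient should be discontinued". No minimum observation period is given for the second branch.

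Four other places bear on these patients:

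- Protocol 12.2 lists, after the procedure on Visit 2: "Record all applicable AEs/SAEs and product complaints".
- Protocol 7.6 records as screen failures consented patients whose ablation procedure was not initiated. It names demographics and the reason for failure as the forms to complete. It does not say whether inserting a probe counts as initiation.
- SAP 6 defines the Safety Analysis Set (SAF) by eligibility and by the device having been utilized during the procedure. It does not say whether puncture without ablation is utilization.
- The Protocol Summary gives the sample size as "N = up to 1500 patients ablated".

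**The concern.** For these patients the puncture is the whole exposure. The plan opens a safety window at probe insertion, then closes it according to whether something was visible while the probe was going in. The AEs of interest in Protocol 17.9 and SAP 8.13 include intrahepatic hematoma, pneumothorax and hemothorax, bleeding, bile leak and infection. It is a clinical inference, not a statement in the documents, that a needle puncture can cause such events and that some need not be apparent during it.

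At stake is the completeness of safety capture in a small group that the protocol's own start rule brings into scope. A secondary matter is the SAF: if these patients count as having had the device utilized, they sit in its denominator with cut-short follow-up.

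**Working it through.** **Step 1: the two rules together.** Reporting starts at first probe placement (13.2), so a punctured patient is in scope. Reporting ends at Visit 14 or early withdrawal (13.2). Section 7.7 discontinues the patient when no AE occurred during puncture. An event first appearing after that point falls outside the required period. Section 13.2 speaks of early withdrawal and 7.7 of discontinuation, but the 7.7 note sits under text on the investigator withdrawing a patient, and early withdrawal is recorded on the Subject Completion/Discontinuation form. Reading the two as the same is reasonable. If they differ, the end of reporting for these patients is undefined.

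**Step 2: does any other rule require a later safety contact?**

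| Text | Why it does not close the gap |
|---|---|
| 7.7, efforts to collect AEs at withdrawal | Written for a patient or representative who decides to withdraw |
| 13.2: "Data related to AEs and SAEs will be collected until event resolution, until the event is considered stable" | Follows events already known, not ones that first appear later |
| 13.2: "For retrospectively enrolled patients, the site should review patient medical records (i.e. through chart review) to look for reportable AEs/SAEs" | Retrospective patients only; under 9.3 these had already been ablated |
| 12.2, AE check after the procedure | Catches events up to that check, perhaps up to discharge, since length of stay is a Visit 2 item |
| 12.3, safety assessment by phone | Belongs to follow-up visits that a discontinued patient no longer has |
| 13.3, product complaints | A partial channel; misses a complication nobody attributes to the device |
| 7.6, screen failure | If a site used it here, even less would be kept |

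None of them requires a later contact.

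**Step 3: size.** The documents give no number of prospective patients, no rate of failed ablation and no risk of late puncture complications. Every input below is an assumption, for illustration only:

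- f, share of prospective probe-inserted patients not ablated: 0.01 to 0.03
- d, risk in those patients of a complication after discontinuation: 0.005 to 0.10
- Missed events = N × f × d

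| N | Group, N × f | Missed, low | Missed, high |
|---|---|---|---|
| 500 | 5 to 15 | 500 × 0.01 × 0.005 = 0.025 | 500 × 0.03 × 0.10 = 1.5 |
| 1000 | 10 to 30 | 1000 × 0.01 × 0.005 = 0.05 | 1000 × 0.03 × 0.10 = 3.0 |

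The product f × d is 0.005 to 0.30 percentage points for any N, a 60-fold range.

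**Step 4: what a separate line could show.** With zero events in n patients, the two-sided 95% Clopper-Pearson upper limit is 1 − 0.025^(1/n). For n = 10 it is 30.8%; for n = 30 it is 11.6%. Such a line can only be descriptive.

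**Step 5: the SAF denominator.** If unablated patients enter the denominator and contribute no recorded events, a rate r among ablated patients becomes r × (1 − f). For an assumed r of 10%: 10% × 0.99 = 9.9%, or 10% × 0.97 = 9.7%. This applies to the prospective part of the SAF; retrospective patients, all ablated, would make the shift smaller.

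**The case against.** The strongest reply is that this is a deliberate choice of scope. The 7.7 note addresses exactly this patient and gives a rule for each branch. The registry studies ablated patients and counts its sample that way, the devices are legally marketed, and nothing beyond standard care is done. Ending follow-up of someone who never received the treatment fits that purpose. This stands as far as value goes: it makes the matter small. It does not remove the gap, because 13.0 and 13.2 set the safety scope by probe insertion, not by completed ablation.

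Three stronger readings are tempting, and the documents do not support them.

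- A reader might infer that later complications are barred from the database or never collected. The text only stops requiring them. A site could still report one, and since no timing is set for discontinuation, anything noticed before the form is completed is reportable.
- A reader might infer that the registry's safety rates are biased. Rates among ablated patients do not depend on this rule. The SAF rate could shift slightly, but only if punctured patients count as having had the device utilized, which SAP 6 leaves open. Nor can one assume that the SAF already holds only ablated patients.
- A reader might infer that patients who did have an AE during puncture lose coverage once it resolves. Section 7.7 does not say what happens next, so that is conjecture.

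It is also fair that the remedy may come too late. Planned enrolment was "Enrollment: ~2 years" and the SAP is dated 30 Oct 2025. Enrolment status is not stated.

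**Conclusion.** The point holds as a minor one. Under 7.7 and 13.2, a puncture complication that first appears after discontinuation need not be reported for a prospectively enrolled patient who was punctured, not ablated, and free of AEs during puncture. This rests on treating discontinuation in 7.7 as early withdrawal in 13.2.

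The size cannot be estimated from the documents. The illustrative range in the working shows only that the count is likely to be small if failed ablation is uncommon. No planned conclusion would change. The gain is more complete safety capture in a small group, and a clear statement of who is in the SAF.

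**What to change.** **Protocol 7.7.** Keep every patient with a probe inserted but no ablation in AE and SAE collection, whether or not an AE was seen during puncture, until one phone or chart safety contact covering the time since insertion. The end of the Visit 3 window is one possible deadline; the length is the sponsor's choice. Then discontinue, and follow any open AE to resolution.

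**Protocol 7.6.** State that probe insertion counts as initiating the procedure, so these patients are not filed as screen failures with only demographics and a reason.

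**SAP 6 and 8.13.** State whether a punctured but unablated patient counts as having had the device utilized. Report these patients' AEs on a separate descriptive line with their own denominator, so that they do not enter the main SAF denominator with truncated follow-up.

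**Cost.** The protocol changes need an amendment with prior IRB/EC approval and one extra contact for a few future patients. They do nothing for patients already discontinued, and events after the contact may still be missed. The SAP change is a definition and one table line.

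**If enrolment has closed.** Only the separate line still applies, with a statement in the CSR that required AE reporting stopped at discontinuation for this group.
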